APPENDIX V: PHARMACODYNAMICS (mRNA TRANSCRIPT LEVELS) STUDY FORM

COG Pt ID # _____
Cycle 1, Day 1 Date: _____
Please do not write patient names on this form or on samples.

Patient Weight: _____ kg Body Surface Area: _____ m²

MLN4924 (Pevonedistat) Dose Level: _____ mg/m² MLN4924 (Pevonedistat) Total Daily Dose: _____ mg

In consenting patients, blood samples (2 ml) will be collected in citrate vacutainer tubes at the following time points during Cycle 1 (\pm 10 min): Day 1 (pre-dose) and Day 3 **OR** Day 5 (3 hrs and 6 hrs after the end of MLN4924 [pevonedistat] infusion).

Record the exact time the sample is drawn along with the exact time MLN4924 (pevonedistat) infusion begins and ends on Day 1 and Day 3 **OR** 5.

Blood Sample No.	Time Point	Scheduled Collection Time	Actual Date Sample Collected	Actual Time Sample Collected (24-hr clock)
1	Day 1	Prior to MLN4924 dose	____/____/____	____:____
MLN4924 Dose on Day 1		Date: ____/____/____	Infusion Start Time: ____:____	Infusion Stop Time: ____:____
MLN4924 Dose on Day 3*		Date: ____/____/____	Infusion Start Time: ____:____	Infusion Stop Time: ____:____
2	Day 3*	3 hrs after MLN4924 infusion end time	____/____/____	____:____
3	Day 3*	6 hrs after MLN4924 infusion end time	____/____/____	____:____
MLN4924 Dose on Day 5*		Date: ____/____/____	Infusion Start Time: ____:____	Infusion Stop Time: ____:____
2	Day 5*	3 hrs after MLN4924 infusion end time	____/____/____	____:____
3	Day 5*	6 hrs after MLN4924 infusion end time	____/____/____	____:____

*Blood samples are to be drawn on Day 3 **OR** Day 5, not on both days.

One copy of this Pharmacodynamic Study Form should be uploaded into RAVE. A second copy should be sent with the samples to the address listed in [Section 8.3.6](#). See [Section 8.3](#) for detailed guidelines for packaging and shipping PD – mRNA Transcript Level samples.

Signature: _____
(site personnel who collected samples)

Date: _____

APPENDIX VI-A: PHARMACODYNAMICS (NEDDYLATED PROTEIN ANALYSIS) STUDY BLOOD SAMPLE INSTRUCTIONS

Eligible samples:

Samples should be sent to the [name] lab only if the patient samples meet the following criteria:

- 1) Eligible patients must have an initial absolute blast count of at least 1000 blasts/ μ L. To calculate the absolute blast percentage, multiply the total WBC by the % peripheral blasts:

$$(WBC)(\%) \text{blast}(1000) = \text{absolute blast count}/\mu\text{L}$$

As an example, if the patient has a WBC of 10 and 50% blasts, the absolute blast count is:

$$(10)(.5)(1000) = 5000/\mu\text{L}$$

If the initial % blasts is unknown, send samples only if the total WBC is more than 10 and notify the [name] lab of the % blast as soon as available (contact info provided below). Sample can be batched, but must be received by the [name] lab no later than 72h after collection.

Note: Do not collect NEDDylated Protein Analysis samples if minimal residual disease is < 1%.

Sample collection time points:

	Day 1, Hour 0	Day 1, Hour 10	Day 1, Hour 24	End of Cycle 1
Peripheral Blood	
5 mL total* (before start of IV azacitidine and MLN4924 [pevonedistat] infusion)**
 
 • 3 mL Cell Save • 2 mL heparin 	
5 mL total* (10h following completion of MLN4924 [pevonedistat] infusion)
 
 • 3 mL Cell Save • 2 mL heparin 	
5 mL total* (24h following completion of MLN4924 [pevonedistat] infusion)
 
 • 3 mL Cell Save • 2 mL heparin 	
5 mL total* (same day as bone marrow evaluation)
 
 • 3 mL Cell Save • 2 mL heparin

***Sample Collection:** Collect sample in syringe and send samples in Cell Save tubes (3 mL) and heparin tubes (2 mL). Either lithium heparin or sodium heparin is acceptable. **Do NOT use lithium PST (plasma separator tubes).** Cell Save tubes should have been received upon study activation by the lead CRA at your site. If Cell Save tubes are not available, the 5 mL can be sent in Heparin collection tubes. Do NOT send only Cell Save tubes as the proteasome and NF- κ B analyses can be done only in heparin tubes.

******It is permissible to collect the Day 1, Hour 0 sample after the intrathecal cytarabine dose.

Shipping Note: Samples collected on Friday, Saturday and Sunday can be shipped Monday for Tuesday arrival.

Specimen Requirements:

- Store samples in refrigerator until shipment.
- Cell Save tubes will be provided by the [name] lab to each institution upon IRB approval.

THIS PROTOCOL IS FOR RESEARCH PURPOSES ONLY, SEE PAGE 1 FOR USAGE POLICY

- To obtain more Cell Save tubes, contact the [name] lab at the numbers provided below.
- If the Cell Save tubes are not available, submit entire 5 mL sample in heparin tubes. **Note that the sample integrity is greatly enhanced by the use of Cell Save tubes for 3 mL of the 5 mL material collected.**
- Each sample should be clearly labeled to include the study number (ADVL1712) as well as the treatment ID number and the accession number; along with date and time sample was drawn.
- Please note the WBC and % blasts on the specimen transmittal form below.
- The institutional immunophenotype report should be FAXed to [contact] (or e-mailed) and sent attn.: [name] c/o [name] laboratory. This is a secure FAX and is used only by laboratory personnel. **NOTE:** it is acceptable for blood to be collected from a central line.

Shipping Requirements:

Prior to sample collection, please contact [name] at [contact] or [name]/[name] lab at [contact] for instructions on shipping. Samples should be shipped in a box with a thick styrofoam container (NO clinic-packs). These containers can be found in your pathology department and are frequently received when your department receives antibody shipments. If you do not have access to these storage containers, a Thermo-safe box can be mailed to your site by regular mail. Please contact us before a patient is ready to enroll if you require a box for sample shipment. Shipment of boxes/tubes takes 5-7 business days and will be sent by USPS.

If Thermo-Safe shipping container is not available:

- Place collection tubes in a primary container. Wrap each collection tube separately to protect from breakage during shipment. Place the container in a thick Styrofoam box.
- Please place an **ice pack** around the primary container. During the non-winter months (year round except Christmas Day in Texas) (other parts of the country: April-October) add **additional ice packs** to the Styrofoam box to assure the samples stays cold during shipment.
- Package sample as appropriate for biologic material.

For all samples, including those in ThermoSafe containers:

- **Include ice packs in the ThermoSafe container in the space provided.**
- Include a copy of the Specimen Transmittal Form with each shipment.
- **If possible, please FAX the bone marrow immunophenotype report with the first peripheral blood sample.** If this is not possible, please send the report that day via [contact]) or email to [name] at [contact] and [name] at [contact] (Please strip HPI identifiers)
- **Ship the sample by Federal Express Priority Overnight delivery to:**

[name] c/o [name]
[name]
[name]
Baylor College of Medicine
[name]
[contact]

Courier information:

- Notify [name] or [name] lab representative prior to shipment of the sample. [contact]. Please email the Fed-Ex tracking number to the email addresses above.
- If possible, do not ship samples for delivery on a weekend or holiday. Weekend samples can be mailed Monday for Tuesday delivery.

**APPENDIX VI-B: PHARMACODYNAMICS (NEDDYLATED PROTEIN ANALYSIS) STUDY
FORM – BLOOD SAMPLES**

COG Pt ID # _____ Cycle 1, Day 1 Date: _____
Please do not write patient names on this form or on samples.

Patient Weight: _____ kg Body Surface Area: _____ m²

MLN4924 (Pevonedistat) Dose Level: _____ mg/m² MLN4924 (Pevonedistat) Total Daily Dose: _____ mg

WBC: _____ /µL % Blasts: _____ %

In consenting patients, blood samples (5 ml) will be collected in Cell Save tubes (3 ml) and heparinized tubes (2 ml) at the following time points during Cycle 1 (\pm 10 min): Day 1 (prior to IV azacitidine and MLN4924 [pevonedistat] dose, 10 hrs after the end of MLN4924 [pevonedistat] infusion, and 24 hrs after the end of MLN4924 [pevonedistat] infusion), and at the end of Cycle 1 on the same day as bone marrow evaluation.

Record the exact time the sample is drawn along with the exact time MLN4924 (pevonedistat) infusion begins and ends on Day 1.

Blood Sample No.	Time Point	Scheduled Collection Time	Actual Date Sample Collected	Actual Time Sample Collected (24-hr clock)
1	Day 1	Prior to MLN4924 dose	____/____/____	____:____
MLN4924 Dose on Day 1		Date: ____/____/____	Infusion Start Time: ____:____	
			Infusion Stop Time: ____:____	
2	Day 1	10 hrs after MLN4924 infusion end time	____/____/____	____:____
3	Day 1	24 hrs after MLN4924 infusion end time	____/____/____	____:____
4	End of Cycle 1	Same day as bone marrow evaluation	____/____/____	____:____

One copy of this Pharmacodynamic Study Form should be uploaded into RAVE. A second copy should be sent with the samples to the address listed in [Section 8.4.6](#). See [Section 8.4](#) for detailed guidelines for packaging and shipping PD – mRNA Transcript Level samples.

Signature: _____ Date: _____
(site personnel who collected samples)

THIS PROTOCOL IS FOR RESEARCH PURPOSES ONLY, SEE PAGE 1 FOR USAGE POLICY

**APPENDIX VII: PHARMACODYNAMICS (NEDDYLATED PROTEIN ANALYSIS) STUDY
FORM – BONE MARROW SAMPLES**COG Pt ID # _____ Cycle 1, Day 1 Date: _____
Please do not write patient names on this form or on samples.Patient Weight: _____ kg Body Surface Area: _____ m²MLN4924 (Pevonedistat) Dose Level: _____ mg/m² MLN4924 (Pevonedistat) Total Daily Dose: _____ mg

WBC: _____ /µL % Blasts: _____ %

In consenting patients, bone marrow samples (2-3 ml) will be collected in heparinized tubes at the following time points: pre-study, and at the end of Cycle 1 on the same day as bone marrow evaluation.

Record the exact time the sample is drawn.

Blood Sample No.	Time Point	Scheduled Collection Time	Actual Date Sample Collected	Actual Time Sample Collected (24-hr clock)
1	Pre-study	Pre-study	____ / ____ / ____	____ ____ : ____ ____
2	End of Cycle 1	Same day as bone marrow evaluation	____ / ____ / ____	____ ____ : ____ ____

One copy of this Pharmacodynamic Study Form should be uploaded into RAVE. A second copy should be sent with the samples to the address listed in [Section 8.4.6](#). See [Section 8.4](#) for detailed guidelines for packaging and shipping PD – mRNA Transcript Level samples.

Signature: _____ Date: _____
(site personnel who collected samples)

THIS PROTOCOL IS FOR RESEARCH PURPOSES ONLY, SEE PAGE 1 FOR USAGE POLICY

APPENDIX VIII-A: THERAPY DELIVERY MAP FOR CYCLE 1

Therapy Delivery Map – Cycle 1

This Therapy Delivery Map (TDM) relates to Cycle 1. Each cycle lasts 35 days.

Patient COG ID number

DOB

Criteria to start each cycle are in [Section 5.3](#). Extensive treatment details are in [Section 5.2](#).

This TDM is on 4 pages.

DRUG	ROUTE	DOSAGE	DAYS	IMPORTANT NOTES
IT Cytarabine (ARAC) (all patients)	Intrathecal (IT)	Age-based dosing: Age (yrs) Dose < 1 20 mg 1-1.99 30 mg 2-2.99 50 mg ≥ 3 70 mg	0	Given at the time of diagnostic lumbar puncture OR Day 0.
IT Cytarabine (CNS 2 or 3 patients)*	IT	Age-based dosing: Age (yrs) Dose < 1 20 mg 1-1.99 30 mg 2-2.99 50 mg ≥ 3 70 mg	Twice weekly	A minimum of 4 and a maximum of 6 (count includes day 0 IT) intrathecal treatments may be given. The choice between IT Cytarabine OR IT Triples for patients with CNS 2 or 3 is up to the treating physician's discretion.
IT Triples (Methotrexate/ Hydrocortisone /Cytarabine) (CNS 2 or 3 patients)*	IT	Age-based dosing: Age (yrs) Dose < 1 MTX: 7.5 mg, HC: 7.5 mg, ARAC: 15 mg 1-1.99 MTX: 8 mg, HC: 8 mg, ARAC: 16 mg 2-2.99 MTX: 10 mg, HC: 10 mg, ARAC: 20 mg 3-8.99 MTX: 12 mg, HC: 12 mg, ARAC: 24 mg ≥ 9 MTX: 15 mg, HC: 15 mg, ARAC: 30 mg	Twice weekly	A minimum of 4 and a maximum of 6 (count includes day 0 IT) intrathecal treatments may be given. The choice between IT Cytarabine OR IT Triples for patients with CNS 2 or 3 is up to the treating physician's discretion.
Azacitidine (AZA)	IV over 15 minutes	Age-based dosing: Age (yrs) Dose < 1 2.5 mg/kg/dose ≥ 1 75 mg/m ² /dose	1-5	On days 1, 3, and 5, administer before MLN4924 (pevoneditat) infusion. See below for timing.
MLN4924	Intravenous (IV)	Patients < 1 year of age:	1, 3, 5	Administer 30-60 minutes after completion

THIS PROTOCOL IS FOR RESEARCH PURPOSES ONLY, SEE PAGE 1 FOR USAGE POLICY

(Pevonedistat)	over 1 hour	Dose Level -1: 10 mg/m ² Dose Level 1: 15 mg/m ² Patients \geq 1 year of age: Dose Level -1: 15 mg/m ² Dose Level 1: 20 mg/m ²		of azacitidine.
Fludarabine (FLU)	IV over 30 minutes	Age-based dosing: Age (yrs) Dose < 1 1 mg/kg/dose \geq 1 30 mg/m ² /dose	6-10	
Cytarabine (ARAC)	IV over 1-3 hours	Age-based dosing: Age (yrs) Dose < 1 67 mg/kg/dose \geq 1 2000 mg/m ² /dose	6-10	Use eye drops as described in Section 5.2 . To begin 4 hours after the start of the fludarabine infusion.

*CNS2 and CNS 3 patients will receive additional IT cytarabine OR IT triples 2x/weekly until the CNS is clear of blasts on 2 consecutive LPs, with a minimum of 4 IT cytarabine OR IT Triples doses administered. Days of therapy may vary depending on scheduling.

Ht _____ cm

Wt _____ kg

BSA _____ m²Dose Level _____ mg/m²

Date Due	Date Given	Day	IT* ARAC _____ mg	IT* Triples _____ mg	AZA _____ mg	MLN4924 (Pevonedistat) _____ mg	FLU _____ mg	ARAC _____ mg	Studies
Enter calculated dose above and actual dose administered below									
		Pre-	mg						a - m, p
		1			mg	mg			e, n, o, p, q
		2			mg				
		3			mg	mg			e, n, p, q
		4			mg				
		5			mg	mg			e, n, p, q
		6					mg	mg	
		7					mg	mg	

THIS PROTOCOL IS FOR RESEARCH PURPOSES ONLY, SEE PAGE 1 FOR USAGE POLICY

		8	mg*	mg*			mg	mg		a,
		9					mg	mg		b,
		10					mg	mg		d,
		11								f,
		12								g,
		13								p
		14								
		15	mg*	mg*						a,
		16								b,
		17								d,
		18								f,
		19								g,
		20								p
		21								
		22	mg*	mg*						a,
		23								b,
		24								d,
		25								f,
		26								g,
		27								p
		28								
		29								a,
		30								b,
		31								d,
		32								f,
		33								g,
		34								p
		35								

*CNS2 and CNS 3 patients will receive additional IT cytarabine OR IT triples 2x/weekly until the CNS is clear of blasts on 2 consecutive LPs, with a minimum of 4 IT cytarabine OR IT triples doses administered. Days of therapy may vary depending on scheduling.

THIS PROTOCOL IS FOR RESEARCH PURPOSES ONLY, SEE PAGE 1 FOR USAGE POLICY

Required Observations in Cycle 1

All baseline studies must be performed prior to starting protocol therapy unless otherwise indicated below.

- a. Hx/Wt /Ht/BSA. Prior to Cycle 1 and every week during Cycle 1.
- b. Physical exam (including VS). Prior to Cycle 1 and every week during Cycle 1.
- c. Performance Status. Prior to Cycle 1.
- d. CBC/diff/platelets. Prior to Cycle 1 and twice weekly during Cycle 1.
- e. Pharmacokinetics. In patients ≤ 10 kg, samples to be collected on Day 1 and Day 5 pre-MLN4924 (pevoneditstat) dose, at the end of MLN4924 (pevoneditstat) infusion, and at 4 – 6 hours, and 24 hours after the end of MLN4924 (pevoneditstat) infusion. In patients > 10 kg, samples to be collected on Day 1 pre-MLN4924 (pevoneditstat) dose, at the end of MLN4924 (pevoneditstat) infusion, and at 1, 2, 4, 6 – 8, and 24 hours after the end of MLN4924 (pevoneditstat) infusion; on Day 3 pre-MLN4924 (pevoneditstat); and on Day 5 pre-MLN4924 (pevoneditstat) dose, at the end of MLN4924 (pevoneditstat) infusion, and at 1, 2, 4, 6 – 8, 24, and 48 **OR** 72 hours after the end of MLN4924 (pevoneditstat) infusion. See [Section 8.2](#) for details.
- f. Electrolytes including Ca^{++} , Mg^{++} , PO_4 . Prior to Cycle 1 and weekly during Cycle 1.
- g. Creatinine. Prior to Cycle 1 and weekly during Cycle 1.
- h. Albumin. Prior to Cycle 1.
- i. Pregnancy test. Prior to Cycle 1.
- j. ECHO or gated radionuclide study. Prior to Cycle 1.
- k. EKG. Prior to Cycle 1.
- l. Bone marrow aspirate and/or biopsy. Prior to Cycle 1 and at the end of Cycle 1.
- m. CSF for cell count, cytospin. Prior to Cycle 1 and at the end of Cycle 1.
- n. Pharmacodynamics (mRNA Transcript Levels). Optional samples to be collected on day 1 pre-MLN4924 (pevoneditstat) dose and on day 3 **OR** day 5 at 3 hours and 6 hours after the end of MLN4924 (pevoneditstat) infusion. See [Section 8.3](#) for details.
- o. Pharmacodynamics (NEDDylated Protein Analysis). Optional samples to be collected on day 1 pre-MLN4924 (pevoneditstat) dose, and at 10 hours and 24 hours after the end of MLN4924 (pevoneditstat) infusion. An additional sample is to be collected at the end of Cycle 1 on the same day as bone marrow evaluation. See [Section 8.4](#) for details.
- p. ALT, AST, Bilirubin. Prior to Cycle 1, prior to each dose of MLN4924 (pevoneditstat), and then weekly.

ADVL1712

THIS PROTOCOL IS FOR RESEARCH PURPOSES ONLY, SEE PAGE 1 FOR USAGE POLICY

q. Vital signs. Prior to each dose of MLN4924 (pevonodistat).

This listing only includes evaluations necessary to answer the primary and secondary aims. OBTAIN OTHER STUDIES AS REQUIRED FOR GOOD CLINICAL CARE.

Comments

(Include any held doses, or dose modifications)

Cycle 1

APPENDIX VIII-B: THERAPY DELIVERY MAP FOR CYCLE 2

Therapy Delivery Map – Cycle 2
 
This Therapy Delivery Map (TDM) relates to Cycle 2. Each cycle lasts 35 days.
	
Patient COG ID number _____
 
DOB _____

---	---

Criteria to start each cycle are listed in [Section 5.3](#). Extensive treatment details are in [Section 5.2](#).

This TDM is on 3 pages.

DRUG	ROUTE	DOSAGE	DAYS	IMPORTANT NOTES
IT Cytarabine (ARAC) (all patients)	Intrathecal (IT)	Age-based dosing: Age (yrs) Dose < 1 20 mg 1-1.99 30 mg 2-2.99 50 mg ≥ 3 70 mg	0	Given at the time of bone marrow aspirate/biopsy at the end of Cycle 1 OR on Day 0 of Cycle 2. See Section 5.2 and Section 5.3 for full details.
Azacitidine (AZA)	IV over 15 minutes	Age-based dosing: Age (yrs) Dose < 1 2.5 mg/kg/dose ≥ 1 75 mg/m ² /dose	1-5	On days 1, 3, and 5, administer before MLN4924 (pevoneditat) infusion. See timing below.
MLN4924 (Pevonedistat)	Intravenous (IV) over 1 hour	Patients < 1 year of age: Dose Level -1: 10 mg/m ² Dose Level 1: 15 mg/m ² Patients ≥ 1 year of age: Dose Level -1: 15 mg/m ² Dose Level 1: 20 mg/m ²	1, 3, 5	Administer 30-60 minutes after completion of azacitidine.
Fludarabine (FLU)	IV over 30 minutes	Age-based dosing: Age (yrs) Dose < 1 1 mg/kg/dose ≥ 1 30 mg/m ² /dose	6-10	
Cytarabine	IV over 1-3	Age-based dosing:	6-10	Use eye drops as described in Section 5.2 .

ADVL1712

THIS PROTOCOL IS FOR RESEARCH PURPOSES ONLY, SEE PAGE 1 FOR USAGE POLICY

(ARAC)	hours	Age (yrs)	Dose			To begin 4 hours after the start of the fludarabine infusion.
		< 1	67 mg/kg/dose			

Ht _____ cm Wt _____ kg BSA _____ m² Dose Level _____ mg/m²

Date Due	Date Given	Day	IT ARAC _____ mg	AZA _____ mg	MLN4924 (Pevonedistat) _____ mg	FLU _____ mg	ARAC _____ mg	Studies
Enter calculated dose above and actual dose administered below								
		Pre-	_____ mg					a - f, h, i, k
		1		_____ mg	_____ mg			g, l
		2		_____ mg				
		3		_____ mg	_____ mg			g, l
		4		_____ mg				
		5		_____ mg	_____ mg			g, l
		6				_____ mg	_____ mg	
		7				_____ mg	_____ mg	
		8				_____ mg	_____ mg	
		9				_____ mg	_____ mg	
		10				_____ mg	_____ mg	
		11						
		12						
		13						
		14						
		15						
		16						
		17						
		18						
		19						
		20						
		21						
		22						g

THIS PROTOCOL IS FOR RESEARCH PURPOSES ONLY, SEE PAGE 1 FOR USAGE POLICY

		23									
		24									
		25									
		26									
		27									
		28									
		29									
		30									
		31									
		32									
		33									
		34									
		35									h – k

Required Observations in Cycle 2

- a. Hx/Wt /Ht/BSA. Prior to Cycle 2.
- b. Physical exam (including VS). Prior to Cycle 2.
- c. CBC/diff/platelets. Prior to Cycle 2.
- d. Electrolytes including Ca⁺⁺, Mg⁺⁺, PO₄. Prior to Cycle 2.
- e. Creatinine. Prior to Cycle 2.
- f. Albumin. Prior to Cycle 2.
- g. ALT, AST, Bilirubin. Prior to each dose of MLN4924 (pevonedistat), then weekly.
- h. ECHO or gated radionuclide study. Prior to Cycle 2 and at the end of Cycle 2.
- i. EKG. Prior to Cycle 2 and at the end of Cycle 2.
- j. Bone marrow aspirate and/or biopsy. At the end of Cycle 2.
- k. CSF for cell count, cytopspin. With day 0 IT and at the end of Cycle 2.
- l. Vital signs. Prior to each dose of MLN4924 (pevonedistat).

This listing only includes evaluations necessary to answer the primary and secondary aims. OBTAIN OTHER STUDIES AS REQUIRED FOR GOOD CLINICAL CARE.

ADVL1712

THIS PROTOCOL IS FOR RESEARCH PURPOSES ONLY, SEE PAGE 1 FOR USAGE POLICY

Comments

(Include any held doses, or dose modifications)

Cycle 2

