8.3.6 Sample Shipping Instructions

Samples should be batched per patient and shipped frozen on dry ice in opaque containers at the end of Cycle 1 according to the lab manual.

8.4 **Pharmacodynamics - NEDDylated Protein Analysis (Optional)**8.4.1 Description of Studies and Assay

Bone marrow and/or peripheral blood will be collected from consenting patients to examine NEDDylated protein degradation and to correlate it with MLN4924

(pevonedistat) response. Peripheral blood samples will only be collected from consenting patients with an initial absolute blast count ≥ 1000 blasts/ μ L (see [Appendix VI-A](#) for details). Bone marrow samples will be collected from consenting patients regardless of initial absolute blast count. Samples will be analyzed by reverse protein lysate array and immune-capillary electrophoresis.

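### Appendix VI-A sets a 72 h receipt deadline for NEDDylation blood samples but allows Monday shipment that delivers Friday samples at about 96 h

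*Combined protocol and SAP*

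**What the plan says.** Section 8.4 describes an optional pharmacodynamic study of NEDDylated proteins, which serves exploratory aim 1.3.2. Blood is drawn in Cycle 1 before the Day 1 azacitidine and pevonedistat doses, 10 h and 24 h after the end of the Day 1 pevonedistat infusion, and at the end of the cycle (Section 8.4.2).

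Appendix VI-A gives these handling rules for the blood samples:

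- Receipt deadline: batching is allowed, but samples must reach the laboratory "no later than 72h after collection".
- Shipping Note: samples drawn on a Friday, Saturday or Sunday "can be shipped Monday for Tuesday arrival".
- Storage: "Store samples in refrigerator until shipment".
- Transit: the consignment goes by an overnight courier service.
- Courier information: "If possible, do not ship samples for delivery on a weekend or holiday", followed by "Weekend samples can be mailed Monday for Tuesday delivery".

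The text available for this review states no exception to the 72 h rule for Friday or weekend samples.

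**The concern.** Both the deadline and the Monday allowance apply to the same blood tubes, and a Friday tube sent by the Monday route cannot meet the deadline. The one obvious route that would meet it, Friday dispatch for Saturday delivery, is the kind of delivery that the courier text asks sites to avoid where they can. A site following the guidance is therefore steered towards missing the deadline.

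The assay compares samples from the same patient before and after dosing. If one sample waits days longer than another, storage time is mixed with the contrast of interest. The data are also few: Section 11.1 anticipates 23 patients, and blood is taken only from those who consent and start with at least 1000 blasts/µL. The plan does not say how a sample received after 72 h is to be treated.

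**Working it through.** **Inputs.** The 72 h limit and the collection days (Friday, Saturday, Sunday) with Monday dispatch and Tuesday arrival come from Appendix VI-A. The documents give no clock times. The last column below therefore assumes draws between 08:00 and 22:00 and arrivals between 09:00 and 17:00. The whole-day range needs no such assumption.

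**Formula.** Elapsed hours = 24 × (days from collection to Tuesday) + (arrival clock time − collection clock time).

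The clock-time difference lies strictly between −24 h and +24 h. Under the assumed hours it runs from 9 − 22 = −13 h to 17 − 8 = +9 h.

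| Drawn | Same clock time | Whole-day range | Assumed hours | Against 72 h |
|---|---|---|---|---|
| Friday | 4 × 24 = 96 h | over 72 to under 120 h | 83 to 105 h | always late |
| Saturday | 3 × 24 = 72 h | over 48 to under 96 h | 59 to 81 h | late if the arrival hour is after the draw hour |
| Sunday | 2 × 24 = 48 h | over 24 to under 72 h | 35 to 57 h | always in time |

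The extreme Friday case, drawn at 23:59 and received at 00:00 on Tuesday, is 72 h 1 min and still late.

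**The alternative route.** Friday dispatch by overnight courier arrives on Saturday: 24 h at the same clock time and under 48 h at most, so it complies.

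**Storage time within a patient** (same clock times, ignoring the short azacitidine and pevonedistat infusions):

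- Thursday start, pre-dose sample shipped at once: received Friday at about 24 h. The 24 h post-infusion sample falls on Friday and, held to Monday, is received at about 96 h. The post-dose sample has waited about 96 − 24 = 72 h longer.
- Friday start, all samples shipped together on Monday: the pre-dose sample is received at about 96 h and the 24 h sample, drawn on Saturday, at about 72 h. Here the baseline has waited about 24 h longer.

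The imbalance can therefore run in either direction.

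**The case against.** Several points can fairly be made against this.

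- The Monday route is permitted, not required. Weekend delivery is discouraged only where possible, and sites are told to contact the laboratory about shipping before they collect. Friday cases could be settled one by one. This stands as mitigation, but the two written rules still disagree.
- The 72 h sentence follows one about samples whose blast percentage is unknown, and the Shipping Note could be read as a specific exception. The 72 h wording is general, however, and the note does not present itself as an exception. Even on the narrow reading the conflict remains for those samples.
- The courier text speaks of weekend samples, which need not include Friday. That is right: the Friday conflict rests on the Shipping Note alone.
- The study forms refer to a Section 8.4.6 that was not in the text available here. It should be checked for further shipping rules.
- Draw times are already recorded and the courier tracking number is emailed to the laboratory. That would help to reconstruct receipt time, but the Appendix VI-B form has no field for it.

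Three stronger readings are tempting and not supported:

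- **That 72 h is the assay's stability limit.** The documents word it only as a receipt deadline and give no stability data.
- **That storage loss would mimic a drug effect.** No degradation data for refrigerated samples are given, and the direction depends on which sample waits longest. With a Friday start and one Monday shipment the baseline waits longest, so a loss in storage could hide a post-dose fall.
- **That a known share of samples is affected.** Thursday and Friday starts put at least one Day 1 series draw on a Friday, which is 2 of 5 weekday starts (40%) or 2 of 7 days (29%). These are shares of start days, not of late samples. They assume evenly spread starts, imply breaches only if every site uses the optional route, and leave out the end-of-cycle sample.

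**Conclusion.** Appendix VI-A contradicts itself on the handling of NEDDylation blood samples. Every Friday sample sent by the permitted Monday route misses the 72 h receipt deadline, by about 24 h at equal clock times (96 − 72). A Saturday sample misses it when Tuesday arrival is later in the day than collection was. Sunday samples comply. The Friday and Sunday results need no assumption about clock times, only that the parcel arrives on Tuesday.

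How many samples would be late cannot be estimated, because the documents give neither the start days nor how often sites would use the allowance. Whether a late sample is unfit for assay is also not stated. The conflict is shown for blood only, since both rules sit in the blood sample instructions and not in the bone marrow form.

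The point is minor. It affects an optional, exploratory, descriptive analysis and has no bearing on the primary or secondary aims.

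**What to change.** Ask the laboratory which limit holds for refrigerated blood, then make the text agree in one of two ways:

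1. **Keep 72 h.** Remove Friday from the Monday allowance and arrange Saturday receipt for those samples, amending the courier text on weekend delivery to match. Keep Saturday samples in the allowance only where Tuesday arrival will be no later in the day than the draw. Otherwise agree an earlier receipt: Monday at the same clock time would be 48 h.
2. **Restate the limit**, if the laboratory confirms that a longer refrigerated hold is acceptable. The new figure must cover the Friday route, whose whole-day bound is just under 120 h.

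In either case add receipt date and time to the data collected, flag samples received beyond the limit, and give the descriptive summary with and without them. Declining to collect Friday samples would also remove the conflict, but it discards scarce paired data and is not recommended.

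The cost is a few lines in Appendix VI-A, one data field, some Saturday-delivery arrangements under the first option, and one additional descriptive summary.
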